1.2 Rationale

Mexiletine hydrochloride (CAS ID: 5370-01-4) is a class 1b anti-arrhythmic agent, based on the Vaughan Williams classification, with local anaesthetic properties, similar in structure and activity to lidocaine (lignocaine) and flecainide. As described in the Ph. Eur. Monograph (2008), mexiletine hydrochloride is a white or almost white, crystalline powder. It exhibits polymorphism. It is freely soluble in water and in methyl alcohol; sparingly soluble in dichloromethane. A 10% solution in water has a pH of 4.0 to 5.5.

[figure not shown]

Figure 1 Chemical Structure of Mexiletine HCl (Source: ChemID Plus)

Mexiletine was initially developed as a treatment for ventricular arrhythmias with subsequent use in long QT syndrome (Heatwole *et al.*, 2013; Sarret *et al.*, 2024). However, after the marketing withdrawal of Boehringer Ingelheim's Mexitil[®] (indication: ventricular arrhythmias) in 2009, there was a significant shortage of supply of licensed mexiletine products in the EU. The originator product was withdrawn from the market because newer active substances superseded the use of mexiletine in the treatment of ventricular arrhythmias.

Despite the shortage, mexiletine gained acceptance as an effective anti-myotonia therapy in both dystrophic and non-dystrophic myotonia (that is, for both the chloride and sodium channelopathies) (Kwiecinski *et al.*, 1992; DGN, 2012; Heatwole *et al.*, 2013; Sarret *et al.*, 2024). Some availability of mexiletine for treatment of myotonic disorders was based on a named patient basis although often associated with supply issues. Therefore, based on the unmet need and the strong evidence for use of mexiletine for treatment of myotonic disorders, an application for marketing authorisation was submitted by the centralised procedure in June 2017 and approved for use throughout the EU in December 2018. Namuscla® containing mexiletine HCl as active substance is currently indicated for the symptomatic treatment of myotonia in adult patients with non-dystrophic myotonic disorders.

The currently approved strength for Namuscla is 200 mg mexiletine HCl formulated as hard capsules for oral use containing 167 mg of mexiletine (NaMuscla SmPC, 2023). The recommended starting dose of mexiletine in adults is 167 mg daily (1 capsule per day). After at least 1 week of treatment, based on the clinical response, the daily dose can be increased to 333 mg daily (2 capsules per day). After at least 1 further week of treatment, based on clinical response, dose can be further increased to 500 mg daily (3 capsules per day). Maintenance treatment is between 167 mg – 500 mg daily (1 to 3 capsules per day), according to the intensity of symptoms and the clinical response, taken regularly throughout the day. The adult daily dose should not exceed 500 mg/day (NaMuscla SmPC, 2023).

As well as the approved 200 mg strength, new paediatric formulations of NaMuscla® were developed consisting of 75 mg and 100 mg strengths with identical qualitative composition to the 200 mg strength. These strengths are not yet authorized. The line extension application is expected to be submitted in April 2025.

Despite reported use and limited data from case studies in the paediatric population, the safety and efficacy of mexiletine in this paediatric population have not yet been established. A recent mini-review of the use of mexiletine in children concluded that special attention by health authorities was needed to maintain access to mexiletine in rare paediatric diseases and further paediatric research was required (Sarret *et al.*, 2024). They specifically mention that off-label

registries for the use of mexiletine in children, especially younger than 6 years, are also required in neuromuscular disorders. The authors admit that although the drug has no proven paediatric indication it has been used in various rare paediatric conditions since the 1970s including heart disorders, neuromuscular diseases, epileptic seizures and pain disorders. Mexiletine has long been reported to be useful in paediatric cardiology and paediatric neurology, with a usual dose ranging between 3 to 15 mg/kg/day (see also section 1.4 Regulatory background).

Observational or low interventional studies, aimed at collecting comprehensive data (Lagrue et al., 2019), even if limited to one single country and to DM1, provide valuable information on which data in children remains scant. In collaboration with the French Child Neurology Society this study included 314 paediatric patients who were recruited in 24 paediatric neuromuscular reference centres across France. The patients were classified as congenital (from birth to 1 year of age; N=155), infantile (between 1 and 10 years of age; N=88) and juvenile (aged 10 -18 years; N=38). The study collected epidemiologic, genetic and clinical data and lasted about 6 years to complete. The clinical data collected and tests performed were dependent on the patient's age group. Outcomes from such studies prove that there are still unmet medical needs with serious consequences in the paediatric myotonias field and that drugs that have proven safe and efficacious in adults to the point of clinical and regulatory approval (NaMuscla SmPC, 2023) deserve to be evaluated for risk-benefit assessment as well as in their use in paediatric populations.

1.3 Risk-Benefit Assessment

The major goal of mexiletine treatment is to alleviate muscle stiffness and thereby decrease associated pain and fatigue and increase movement and patient quality of life. In 2018 the CHMP gave a positive benefit-risk of mexiletine for the symptomatic treatment of myotonia in the adult NDM patient population. In particular, it was concluded that the efficacy and safety of mexiletine in NDM was demonstrated in the randomised, placebo-controlled MYOMEX study. The MYOMEX study included 25 patients with NDM (13 myotonia congenita (MC) and 12 paramyotonia congenita (PC); that is chloride and sodium channelopathies, respectively); with mexiletine dosing 200 mg/day for 3 days, 400 mg/day for 3 days and 600 mg/day for an additional 12-16 days; and total treatment duration of 19 days (mean 19 days, median 19 days, range 10-21 days). However, the CHMP considered that the submitted literature references and data did not firmly support the clinical relevance of the observed changes in muscle stiffness in DM type 1 patients. Additionally, while muscle stiffness is considered to be important disabling medical problem for patients with NDM, it is considered less disabling for patients with DM type 1. Despite this, the efficacy of mexiletine for the symptomatic treatment of myotonic disorders has also been described in several reports of offlabel use and/or clinical studies in the DM target population such that mexiletine is usually considered the first line treatment for these conditions despite being off label.

In general, the safety profile of mexiletine is well known in adults through many years of use as an anti-arrhythmic agent (it was withdrawn from use in this indication for commercial and not for safety reasons).

In one of the registry studies (Wahbi *et al.*, 2017), DM1 patients had a cumulative 3.8 % incidence of sudden death due to arrhythmia and other cardiac causes over a median 10 years follow up. Mexiletine is known to be able to trigger arrhythmia or aggravate an existing arrhythmia and thus patients known to be at risk are excluded from the trial and contraindicated

in the product labelling. Similarly, the screening visit and safety assessments also closely monitor the risk of arrhythmia and cardiac safety, through ECG for example, and cardiac safety is an important consideration for paediatric dose titration. Mexiletine is contraindicated in case of heart failure with mid-range (40-49%) and reduced (<40%) ejection fraction because of the proarrhythmic effects. An increased mexiletine plasma concentration is a risk factor for patients with cardiac abnormalities or prone to such abnormalities, thus the SmPC recommends additional cardiac monitoring after any dose increase which has been applied in the study protocol to reduce risks.

Efficacy and safety data in special populations such as elderly and paediatric subjects have not yet been clearly demonstrated, although several reports describing use have been published (See section 1.3) (Lagrue *et al.*, 2019; Sarret *et al.*, 2024). Lupin has also conducted an openlabel, non-comparative study to evaluate the steady-state pharmacokinetics, safety, and efficacy of mexiletine in adolescents and children with myotonic disorders (MEX-NM-301). To date, MEX-NM-301 has collected evaluable data for PK, efficacy and safety from 7 subjects aged 12 less than 18 years, and 3 subjects aged 6 to less than12 years (10 subjects in total). This study is still ongoing. In addition, Lupin is also conducting MEX-NM-303, an open-label extension study to evaluate the long-term safety and efficacy of mexiletine in paediatric patients with myotonic disorders who have completed the MEX-NM-301 study. This study is also ongoing.

The objective of this registry in paediatric patients aged from birth to 6 years is to assess safety, tolerability and efficacy (exploratory) data in the paediatric population under routine regular clinical practice. However, given the rareness of the condition, there is no specific hypothesis testing or statistical assumptions and data will be collected and analysed descriptively.

Overall, it can be concluded that:

- Myotonic disorders refer to conditions (DM1, DM2 and NDM) that are rare (orphan) diseases with no known cure and only symptomatic treatment, therefore there is a great unmet need for this patient population.
- Mexiletine is the only approved product for symptomatic treatment of NDM in adults although there is evidence to suggest that it also can have benefits to symptomatic DM patients. Therefore, patients enrolled in the study are expected to have some benefit in their myotonic symptoms from the treatment.
- Safety of mexiletine has been determined in adults when used in antiarrhythmic indications as well as in some studies of patients with myotonic disorders. Risk minimisation measures have been proposed in the study design to address the known safety concerns.
- As there is very limited safety data in the paediatric population, it is considered essential to generate relevant data to inform dosing and labelling requirements.
- Registries or non-interventional studies like this one allows to establish standard of care and assess the value and the safety of medications like mexiletine in the paediatric population.

Therefore, the risk-benefit balance of the study is considered positive and supports the conduct of this registry and the continued clinical development of mexiletine.

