Protocol No. MEX-NM-401 Version No.: 1.0 Dated: May 30th 2024

Study Drug Dose, Dosage Form, and Mode of Administration

Dosing recommendations for oral administration of mexiletine capsule are still being established and are currently estimated according to the child's body weight. Dosing in this registry study is at the discretion of the treating physician and the clinical response of the patient. No per protocol specific dosing instructions are provided to the treating physician. The Sponsor of this non-interventional registry study is trying to understand how the drug is currently being used in this disease and population and try to establish a benefit:risk assessment.

Administration will be via the oral route, using either capsules or opening and sprinkling contents on food/drink according to the child's age and ability.

Dose suitability with regard to sprinkling contents on food/drink will be assessed.

Study Endpoints and Outcome Variables:

As permitted by clinical practice and patient's age, the following assessments are proposed:

- To assess the efficacy of mexiletine for the treatment of myotonic disorders as assessed by the clinician including as follows (where applicable).
 - Muscle strength measured using the modified Medical Research Council (MRC) scale to evaluate neck flexors, shoulder abductors, elbow flexors and extensors, wrist extensors, finger flexors, hip flexors, knee flexors and extensors, posterior foot flexors and plantar flexors.
 - Clinical Global Impression (CGI) Scores given to caregivers and assessed by the investigators
- To assess long-term safety
 - Number and frequency of adverse events (AEs), serious adverse events (SAEs) and AE leading to treatment discontinuation, throughout the study while on treatment with mexiletine
 - Incidence of adverse events of special interest (AESI), namely:
 - Severe Cutaneous Adverse Reactions (SCARs).
 - Cardiac arrhythmia.
 - Increased frequency of seizure episodes in patients with epilepsy.
- To assess the different routes of administration and formulations of mexiletine used according to clinician's preferences
- To assess safety and efficacy of mexiletine dosing formulations used
- To assess dose and treatment compliance as well as acceptability and palatability of different modes of administration.

Statistical Methods

Sample Size

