4 TREATMENT OF PATIENTS AND INVESTIGATIONAL PRODUCT MANAGEMENT

4.1 Treatment of Patients

4.1.1 Dosage and Treatment Regimen

Mexiletine will be used at the discretion of the treating physician without protocol mandated instructions or limitations.

Patients should take the study medication as prescribed by the investigator, preferably with food and at the same time daily.

For patients who are not able to swallow capsules, capsule contents to be opened and sprinkled on food or mixed with milk/juice. Details on dosing, formulation, route and mode of administration will be collected by the caregiver in the electronic data capture (EDC).

Each patient/caregiver will be provided with sufficient prescriptions until next clinically indicated study visit.

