4.1.1.1 Dose Escalation

Any dose escalation -or reduction- will be at the discretion of the treating physician and will be duly collected in the CRF.

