5 STUDY PROCEDURES

All patients/ caregivers / parents or legal representatives must provide their written informed consent and assent before any assessments or evaluations required by the study are performed. All screening assessments must be completed within 2 weeks of informed consent.

The evaluations and assessments during the study will be performed according to routine clinical practice or as necessary for each individual patient according to the treating physician. Consulted clinical experts have recommended that according to standards of care visits are usually performed with a frequency no longer than every 6 months.

There will be a screening visit to ensure the patient complies with all the participation criteria.

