5.1 Screening Visit – V0 (Maximum 2 weeks)

The screening procedures will include recording the following parameters which typically have already been collected in the patient's medical history:

- 1. Obtaining written informed consent/ assent as per regulatory requirement
- 2. Patient demographics and anthropometric measurements (age, gender, ethnicity, height, weight)
- 3. Vital signs, including blood pressure (BP), heart (pulse) rate (HR)
- 4. Current medical condition: Type of myotonic disorder (genetic diagnosis), age of symptom onset, family history of myotonic disorders.
- 5. Signs and symptoms of myotonia as documented in medical history.
- 6. Clinical myotonia evaluation appropriate to patient's age and treating physicians standard clinical practice including proposed efficacy assessments and quality of life evaluations, where performed.
- 7. Review of inclusion/exclusion criteria
- 8. Medical history of:
 - Neurological disorders (Seizure, Epilepsy, Vertigo, Headache, Paraesthesia, Dysgeusia, Ataxia)
 - Gastrointestinal disorders (Abdominal pain, Nausea, Vomiting, Diarrhoea, Constipation, Intestinal ulcer, GI bleeding, Dysphagia, Oesophageal ulceration)
 - Renal or hepatic disorders
- 9. Any other significant medical history
- 10. History of unprovoked falling and stumbling, fractures
- 11. History of swallowing difficulties and/or laryngospasm (particularly below 6 months of age) / history of aspirations/ aspirational pneumonia (myotonia of mastication muscles)
- 12. History of hospitalisation due to muscle condition
- 13. History of any cardiac, rhythm disorders.
- 14. Cardiac status at baseline (ECG and echocardiogram (cardiac ultrasound; US), done up to 3 months prior to screening is acceptable. If not done earlier, ECG and echocardiogram to be performed at screening visit)
- 15. Surgical history
- 16. For patients previously prescribed mexiletine, any modification in mexiletine dose/ frequency in addition to the current dose/frequency as prescribed by the treating physician

- 17. History of previous anti-myotonia treatment other than / mexiletine
- 18. Concomitant medications in use (along with dose and frequency)
- 19. Washout for any current/ ongoing medications required/not required
- 20. Collection of known laboratory investigations if performed according to the treating physician regular practice including basic haematology, biochemistry and urinalysis.

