8.5 Electrocardiogram Assessments (ECGs)

A 12-lead ECG will be performed at screening and after screening according to regular clinical practice or at the discretion of the treating physician. Any abnormal findings will be evaluated for clinical significance.

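### Section 1.3 says cardiac monitoring after dose increases is built into the protocol, but no operative section requires it; separately, the entry and stopping QT limits disagree at exactly 450 ms (minor corrections)

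*Protocol*

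**What the plan says.** **Monitoring after a dose increase.** Section 1.3 gives a reason for concern, "An increased mexiletine plasma concentration is a risk factor for patients with cardiac abnormalities or prone to such abnormalities", and then says that "the SmPC recommends additional cardiac monitoring after any dose increase which has been applied in the study protocol to reduce risks".

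The sections that govern conduct read differently:
- Section 4.1.1: "Mexiletine will be used at the discretion of the treating physician without protocol mandated instructions or limitations". The synopsis agrees: "No per protocol specific dosing instructions are provided to the treating physician".
- Section 4.1.1.1: "Any dose escalation -or reduction- will be at the discretion of the treating physician and will be duly collected in the CRF".
- Section 5: "The evaluations and assessments during the study will be performed according to routine clinical practice or as necessary for each individual patient".
- Section 8.5: "A 12-lead ECG will be performed at screening and after screening according to regular clinical practice or at the discretion of the treating physician".
- Section 5.1, on the baseline cardiac work-up: "If not done earlier, ECG and echocardiogram to be performed at screening visit".

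Section 1.4 bases the non-interventional status partly on all diagnostic and monitoring procedures belonging to normal clinical practice.

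**QT limits.** Exclusion 1e, in the synopsis and in section 3.3.2, bars a QT interval above 450 ms. Section 4.1.1.2 lists a QT of 450 ms or more among the criteria for immediate and permanent discontinuation.

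**The concern.** The sentence in section 1.3 is a factual safety statement in the section that concludes the risk-benefit balance is positive. The drug is used off label in children from birth to under 6 years, and the same section says it can trigger or aggravate arrhythmia. An ethics committee member or investigator reading 1.3 would believe that the protocol requires a cardiac check after each dose increase. In fact the physician decides whether to do one.

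The QT point is smaller but concerns a decision threshold. Inclusion criterion 4 admits children already on mexiletine. A treated child with a baseline QT of exactly 450 ms would pass exclusion 1e and at once meet a mandatory stopping rule.

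**Working it through.** The plan gives no figure to reproduce. The check sets the text side by side and compares two inequalities.

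**Step 1. Is a cardiac check after a dose increase required anywhere?**

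| Protocol section | What it fixes | Check tied to a dose increase? |
|---|---|---|
| 4.1.1 Dosage and regimen | Use at physician discretion | No |
| 4.1.1.1 Dose escalation | Changes discretionary, recorded in the CRF | No |
| 5 Study procedures | Assessments by routine practice or individual need | No |
| 5.1 Screening | Baseline ECG and echocardiogram, up to 3 months old accepted | No (baseline only) |
| 8.5 ECGs | ECG at screening; later ones by practice or discretion | No |
| 3.1 Overall design | General exception for extra safety measures and tests | No test or trigger named |
| 8.2 AESI | Careful monitoring for listed events; interruption on heart block | No test or trigger named |

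Sections requiring a cardiac check after a dose increase: 0. ECGs required after screening: 0.

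**Step 2. Which cardiac safeguards does the protocol have?** Five are in the operative text: cardiac assessment at entry (inclusion 5), the cardiac exclusions (1c to 1j), stopping rules with medical monitor review (4.1.1.2), the baseline ECG and echocardiogram (5.1), and arrhythmia as an event of special interest (8.2). The error is confined to one described safeguard.

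**Step 3. Do the entry and stopping criteria match?** Exclusions 1c to 1j pair one to one with the eight bullets of 4.1.1.2:

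| Criterion | Entry (3.3.2) | Stopping (4.1.1.2) | Match |
|---|---|---|---|
| Ventricular tachyarrhythmia | present | present | yes |
| Heart block | PR ≥ 200 ms, QRS ≥ 120 ms | PR ≥ 200 ms, QRS ≥ 120 ms | yes |
| QT | > 450 ms | ≥ 450 ms | **no** |
| Infarction or abnormal Q-waves | present | present | yes |
| Symptomatic coronary disease | present | present | yes |
| Heart failure | EF < 50% | EF < 50% | yes |
| Atrial arrhythmia | present | present | yes |
| Sinus node dysfunction | rate < 50 bpm | rate < 50 bpm | yes |

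8 pairs − 1 mismatch = 7 that agree.

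**Step 4. How large is the QT overlap?** Passing 1e means QT ≤ 450 ms. Meeting the stopping rule means QT ≥ 450 ms. Both hold only at QT = 450 ms, which is one value in whole milliseconds.

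**The case against.** **Applied need not mean mandated.** Section 1.3 does not say required or scheduled. In a registry where monitoring is that of normal practice, a label recommendation can take effect through that practice. Section 3.1 allows extra safety measures, and section 8.2 asks for careful monitoring with no time limit, which covers the period after a dose increase. It stands that cardiac monitoring is not absent and that investigators receive no conflicting instructions. It does not rescue the sentence: a check that the physician may or may not do under routine practice is not something the protocol has applied.

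**The QT point is nearly trivial.** It concerns one value. Such a child must also pass inclusion 5 and exclusion 3, which lets the physician exclude on ECG grounds. The protocol says QT and names no rate correction. If it is uncorrected, and heart rates of 80 to 140 bpm are assumed (the documents give none), Bazett correction gives 450/√(60/80) ≈ 520 ms to 450/√(60/140) ≈ 687 ms, and such a child would hardly be enrolled. A slightly stricter stopping limit also errs on the safe side. All this limits the practical weight. It leaves two limits that disagree where seven parallel criteria agree. A text-extraction fault in the sign cannot be fully ruled out but is unlikely, since the entry limit reads the same in both places.

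**Stronger readings a reader might infer.** One is that cardiac risk minimisation is missing, or that the risk-benefit conclusion falls. The five safeguards in the working contradict this, and known cardiac abnormalities are largely screened out at entry. Another is that the protocol ought to mandate an ECG after each increase. Leaving ECGs to routine practice fits the status claimed in section 1.4, and a mandated extra procedure would strain it. A third is that arrhythmia incidence will be misestimated. Nothing in the document allows such an effect to be sized, and none is claimed.

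**Conclusion.** Both points hold as minor corrections. The clause in section 1.3 describes a safeguard that the protocol does not require: none of the operative sections ties a cardiac check to a dose increase. What is wrong is the sentence, not the choice to follow routine practice. The gap it hides mainly concerns children who are prone to cardiac abnormalities but not excluded. The QT limits contradict each other at one value, and one of them triggers a mandatory, immediate and permanent stop.

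This rests on the protocol text alone. The SmPC was not checked, so what it recommends and lists is taken as the protocol reports it. The safety and monitoring plans that the protocol mentions were not available, and nothing is assumed about their content.

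**What to change.** 1. In section 1.3, keep the statement of what the SmPC recommends and replace the final clause with: *in this registry such monitoring follows the treating physician's routine practice and is recorded when performed*. This agrees with section 3.2, which lists ECG and ejection fraction among the data collected where normal practice permits. Do not add a mandatory ECG.
2. Use one QT limit. By default, set the stopping rule in 4.1.1.2 to above 450 ms. It then matches the contraindication list that the protocol attributes to the SmPC, as the other seven criteria already do. If the clinical team prefers the stricter limit, set exclusion 1e to 450 ms or more in both the synopsis and section 3.3.2.

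**Cost.** One clause and one inequality sign (in two places if the entry limit is changed). The QT edit touches a stopping or entry rule, so it may need ethics committee approval under section 10.3; carry both edits in the next amendment rather than in a separate one. The default makes the stopping rule less strict at one value; the alternative departs from the attributed SmPC list at one value. The corrected 1.3 describes a less protective protocol than the present sentence does and may prompt a question from the ethics committee.
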